### **5.2 Treatment-emergent adverse events**

Treatment emergent AEs are those which start in the on-treatment period. The on-treatment period lasts from the date of first administration of study medication after informed consent to 30 days after the month 12 COVID-19 follow up call.

The date of first administration of study medication is derived as follows:

Cohort 1 (continued siponimod treatment): Because patients eligible for cohort 1 should have stable siponimod treatment before the study, the date of informed consent is used as date of first study medication. Deviations against this assumption will be detected during the data review meeting and monitoring of protocol deviations. If, necessary this derivation will be adapted.

Cohort 2 (interrupted siponimod treatment): Siponimod treatment can be interrupted before or after the informed consent. For patients who interrupted siponimod before informed consent, the date of first study medication is the first siponimod dose after informed consent or the date of first vaccination, whatever is earlier. For patients who interrupted siponimod after informed consent the date of informed consent is the date of first study medication.

Cohort 3: For patients who are treated with a first-line DMT the date of first study medication is derived like in cohort 1. For patients who do not receive any DMT the date of first study medication is the date of first vaccination.

If no month 12 COVID-19 follow-up call is available, the on-treatment period lasts to the date of last visit plus 30 days.

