12.4.1 Safety endpoints

For all safety analyses, the safety set will be used. All listings and tables will be presented by cohort.

Safety summaries (tables, figures) include only data from the on-treatment period which will also be summarized where appropriate (e.g. change from baseline summaries). In addition, a separate summary for death including on treatment and post treatment deaths will be provided. In particular, summary tables for adverse events (AEs) will summarize only on-treatment events, with a start date during the on-treatment period (treatment-emergent AEs).

The on-treatment period lasts from the date of first administration of study treatment to 30 days after the month 12 COVID-19 follow-up call.

Adverse events

All information obtained on adverse events will be displayed by cohort.

The number (and percentage) of participants with treatment emergent adverse events (events started after the first dose of study medication or events present prior to start of double-blind treatment but increased in severity based on preferred term) will be summarized in the following ways:

- by cohort, primary system organ class and preferred term.
- by treatment, primary system organ class, preferred term and maximum severity.

Separate summaries will be provided for study medication related adverse events, death, serious adverse events, other significant adverse events leading to discontinuation, and adverse events leading to dose adjustment.

A participant with multiple adverse events within a primary system organ class is only counted once towards the total of the primary system organ class.

Vital signs

All vital signs data will be listed by treatment group, participant, and visit/time and if ranges are available, abnormalities (and relevant orthostatic changes) will be flagged. Summary statistics will be provided by treatment and visit/time.

Clinical laboratory evaluations

All laboratory data will be listed by treatment group (cohort 1-3), participant, and visit/time and if normal ranges are available abnormalities will be flagged. Summary statistics will be provided by treatment and visit/time.

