### **2.8.1 Adverse events (AEs)**

According to the CSP all adverse events starting in the on-treatment period, i. e. the treatment emergent AEs, are analyzed.

The on-treatment period lasts from the date of first administration of study treatment after informed consent to 30 days after the month 12 COVID-19 follow-up call.

The number (and percentage) of subjects with treatment-emergent adverse events will be summarized in the following ways:

- by treatment group (cohort 1-3), primary system organ class and preferred term.
- by treatment group (cohort 1-3), primary system organ class, preferred term and maximum severity

A subject with multiple AEs within a MedDRA primary system organ class is only counted once towards the total of the primary system organ class.

A subject with multiple AEs within a preferred term is only counted once towards the total of the preferred term class.

Separate summaries will be provided for study medication related AEs, death, SAEs, AEs leading to discontinuation and adverse events leading to dose adjustment.

The absolute and relative frequency of COVID-19 infections is presented.

Deaths and serious adverse events are listed in addition.

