## **4 Change to protocol specified analyses**

The definition for the Efficacy analysis Set was adapted to avoid that non-missing secondary endpoints would be excluded from the efficacy analysis set. For the rate of seroconversion (primary parameter) the patients with missing data are already excluded from the denominator.

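### The protocol defines a treatment-emergent AE in two conflicting ways; the SAP takes the narrower without logging it, so some worsened AEs count in some patients and not in others

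*SAP*

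**What the plan says.** **SAP.** Section 2.8.1 states: "According to the CSP all adverse events starting in the on-treatment period, i. e. the treatment emergent AEs, are analyzed". Section 5.2 repeats the rule: "Treatment emergent AEs are those which start in the on-treatment period". Neither mentions an event that began earlier and became worse. Section 2.8.1 then tabulates these events by cohort, class and term, and again by maximum severity.

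**Protocol 12.4.1.** There are two definitions in the same section. The first says that "summary tables for adverse events (AEs) will summarize only on-treatment events, with a start date during the on-treatment period (treatment-emergent AEs". The second is attached directly to the tables by class, term and severity. It counts events that start after first dose and also "events present prior to start of double-blind treatment but increased in severity based on preferred term".

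**Start of the on-treatment period (SAP 5.2).** For cohort 1, "the date of informed consent is used as date of first study medication", and cohort 3 patients on a first-line DMT are handled the same way. In cohort 2, "For patients who interrupted siponimod after informed consent the date of informed consent is the date of first study medication"; for those who stopped siponimod before consent, "the date of first study medication is the first siponimod dose after informed consent or the date of first vaccination, whatever is earlier". For cohort 3 patients without a DMT it is the date of first vaccination.

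**Change log.** SAP 4 records one departure from the protocol: "The definition for the Efficacy analysis Set was adapted". It says nothing about the AE definition.

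**The concern.** Safety is a secondary objective, and it expressly includes AEs linked to stopping and restarting siponimod. The protocol itself raises the possible return of disease activity after an interruption (1.1) and a possible effect of the vaccine on MS activity (4.5). Worsening of something already present is one plausible form of such harm. A rule based only on start date cannot see it when the event began before the on-treatment period.

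The start of that period also differs between patients. The same clinical course can therefore enter the tables for one cohort and not for another, and it can split cohort 3, which protocol 4.1 presents as the reference group. A reader of the study report would not know this, because the SAP presents its rule as the protocol's and logs no choice between the two definitions.

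**Working it through.** No sample-size or power figure bears on this point, so the check sets the texts side by side and follows one event through the rules.

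**Step 1. Compare the definitions.**
- Protocol 12.4.1, first sentence: start date in the on-treatment period.
- Protocol 12.4.1, table definition: start after first dose, or present earlier and more severe later. The reference point for the second limb is a double-blind phase. The study is open-label, so as written that limb has no usable date.
- SAP 2.8.1 and 5.2: start date only.

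The SAP matches the first protocol definition and omits the second limb of the other.

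**Step 2. Confirm that such an event can be recorded.** Protocol 10.1.1 defines an AE as an occurrence after written consent, and Table 8-1 collects AEs from screening. Screening runs from day -30 to day -3 and can be extended if the patient is not yet eligible for vaccination under local rules (protocol 3). There is therefore a window between consent and first vaccination in which AEs are recorded. Protocol 10.1.1 also requires changes in severity of a detected AE to be assessed at each visit.

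**Step 3. Follow one event.** Take an AE that starts after consent and before first vaccination, and increases in grade after vaccination.

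| Patients | Period opens (SAP 5.2) | Counted under the SAP rule? | Counted with a worsening limb? |
|---|---|---|---|
| Cohort 1 | Consent | Yes, at maximum severity | Yes |
| Cohort 3, on a DMT | Consent | Yes, at maximum severity | Yes |
| Cohort 2, stopped siponimod after consent | Consent | Yes, at maximum severity | Yes |
| Cohort 2, stopped siponimod before consent | First vaccination, or an earlier siponimod dose after consent | No, if it starts before that date | Yes |
| Cohort 3, no DMT | First vaccination | No | Yes |

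**Step 4. Conditions already present at consent.** Protocol 10.1.1 sends these to medical history. Protocol 8.5 requires significant findings after consent to be recorded as AEs if they meet the AE definition, and the SAE definition in 10.1.2 names worsening of a pre-existing condition. For a non-serious worsening, the documents do not say whether it receives its own AE record and start date. If it does, the SAP rule counts it. If it does not, no programming rule can recover it, because no CTCAE grading of medical-history conditions is described.

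**Step 5. Scale.** The documents do not give the number of patients affected. Per patient, the change in a cohort's AE frequency is 1/n:
- n = 20: 1/20 = 5.0 points.
- n = 22 (the planned enrolment per arm): 1/22 = 4.5 points.

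**The case against.** The strongest reply is that the SAP does follow the protocol. One protocol sentence states the start-date rule for the AE summary tables, and the other definition cannot be applied as written. That stands. A reader might infer that the SAP dropped a clear protocol rule; the documents show instead a protocol that contradicts itself and a SAP that chose one side. What remains is that the discarded definition is the one attached to the tables by class, term and severity, and that the choice is not disclosed.

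A reader might also infer that chronic MS symptoms which worsen after vaccination or the siponimod break generally disappear from the safety tables. The documents do not support that. For cohort 1, DMT-treated cohort 3 patients and cohort 2 patients who stop after consent, every AE recorded after consent already falls in the period and is tabulated at its maximum severity. Conditions present at consent are not AE records carrying an old start date. Serious worsening falls within the SAE definition, SAEs and deaths are listed (SAP 2.8.1), and relapses have their own crude annual rate (SAP 2.7.1).

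The affected subgroups are also likely to be small. Inclusion criterion 4 requires no DMT interruption in the 4 weeks before inclusion, and SAP 2.1.1 treats a violated inclusion criterion as a screening failure, so few cohort 2 patients should have stopped before consent. SAP 5.2 nevertheless provides for them. Untreated cohort 3 patients have no siponimod to stop, so for them the issue is worsening after vaccination only.

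Finally, one could assume one to three patients in every cohort and read off 1/20 to 3/20, or 5 to 15 points. No figure in the documents supports those counts, and under SAP 5.2 the start-date rule should lose no recorded AE in cohort 1 or DMT-treated cohort 3.

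**Conclusion.** The point holds in a limited form. Protocol 12.4.1 contains two incompatible definitions, and the SAP adopts the narrower one without saying so in section 4. The consequence that follows from the text alone is uneven counting. AEs that start between consent and the SAP 5.2 date of first study medication, and then worsen, are omitted for untreated cohort 3 patients and for cohort 2 patients who stopped siponimod before consent, but counted for all others.

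The number of patients is unknown and probably small. At about 5 points per patient with 20 per cohort, even one could be visible in a table. This assumes that a worsening is entered as a change in grade of the existing AE and not as a new AE; a new entry dated at the worsening would be counted under either rule.

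A second route, non-serious worsening of a medical-history condition, depends on recording practice that the documents do not state. It is a gap in the instructions, not a demonstrated loss.

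**What to change.** 1. **SAP 2.8.1 and 5.2:** count an AE as treatment-emergent if it starts in the on-treatment period, or if it was recorded before that period and increases in CTCAE grade during it.
2. **Protocol 12.4.1:** align the two definitions, and replace the reference to double-blind treatment with the SAP 5.2 date of first study medication.
3. **Recording:** state that a non-serious worsening of a medical-history condition is entered as a new AE dated at the worsening. A programming flag alone cannot capture these.
4. **SAP 4:** log the choice. If the start-date rule is kept, say so there and give the reason.

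The cost is some wording and a little programming that uses severity data already required for detected AEs. AE frequencies may rise slightly. The change does not give all patients the same period start: an AE before vaccination that never worsens would still count in cohort 1 and not in untreated cohort 3 patients. A table footnote should say so.

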## 5.3 Statistical models

### 5.3.1 Primary analysis

The primary parameter “seroconversion” is derived from the laboratory data as follows:

Seroconversion is achieved, when SARS-CoV-2 neutralizing antibodies were not found (“negative”) at the time of screening but SARS-CoV-2 neutralizing antibodies are found (“positive”) at visit 1, visit 2 respectively visit 3.

### 5.3.2 Key secondary analysis

Not applicable

## 5.4 Rule of exclusion criteria of analysis sets

Deviation ID	Description of Deviation	Exclusion in Analyses
I01	Incl. crit. no. 1 (IFC) violated	Excluded from all analysis Sets
O05	Primary parameter (SARS-2-CoV-2 antibodies at Week 1) is missing	Excluded from denominator to calculate the rate of seroconversion

Table 2 Subject Classification

Analysis Set	PD ID that cause subjects to be excluded	Non-PD criteria that cause subjects to be excluded
all	NA	Not having informed consent;
SAF/Efficacy Analysis Set	NA	Not having any study treatment
Efficacy Analysis Set(s)	NA	Vaccination 1 not done or Vaccination not done with mRNA or Different vaccines at first and 2 nd vaccination or Positive neutralizing SARS-Cov-2 antibodies at screening

